3 SYNOPSIS

Protocol Number:

TLC590A1001

Title:

A Phase I/II, Randomized, Double-blind, Comparator-controlled, Dose-escalation Study to Evaluate the Safety, Pharmacokinetics, and Efficacy of TLC590 for Postsurgical Pain Management Following Inguinal Hernia Repair

Investigational Product:

TLC590 (Ropivacaine Liposome Injectable Suspension)

Study Centers:

Approximately 2 centers in the United States (US)

Phase:

Phase I/II

Objectives:

The primary objective of this study is to evaluate the safety and tolerability of TLC590 for postsurgical pain management in subjects with inguinal hernia repair surgery.

The secondary objectives of this study are:

- To evaluate the pharmacokinetic (PK) profile and dose-exposure relationship of TLC590, as well as the bioavailability as compared with Naropin®.
- To evaluate analgesic efficacy of TLC590 compared with Naropin® for postsurgical pain management in subjects with inguinal hernia repair surgery.
- To evaluate the exposure-response relationship between PK parameters and pain management.

Study Design:

This is a Phase I/II, randomized, double-blind, comparator-controlled, dose-escalation study to assess the safety, PK, and efficacy of single postsurgical application of TLC590 compared with Naropin® via a single infiltrative local administration in adult subjects following inguinal hernia repair surgery.

The study will enroll approximately 64 evaluable subjects who meet all entry criteria across 4 cohorts.

Approximately 16 subjects will be enrolled to each cohort in a 3:1 ratio. Each cohort will comprise 12 subjects receiving a dose of TLC590 and 4 subjects receiving active comparator drug (Naropin® 150 mg; [0.5%, 5 mg/mL]) in accordance with the randomization schedule (as assigned by a centralized interactive web response system [IWRS]) and dose-escalation scheme outlined in the following table.

Cohort	TLC590	Naropin®
Cohort 1 (N = 16)	N = 12: TLC590; 190 mg (10 mL)	N = 4: Naropin®; 150 mg (30 mL)
Cohort 2 (N = 16)	N = 12: TLC590; 380 mg (20 mL)	N = 4: Naropin®; 150 mg (30 mL)
Cohort 3 (N = 16)	N = 12: TLC590; 570 mg (30 mL)	N = 4: Naropin®; 150 mg (30 mL)
Cohort 4 (N = 16)	N = 12: TLC590; 760 mg (40 mL) OR N = 12: TLC590; 475 mg (25 mL); if the TLC590 570 mg (30 mL) dose is not tolerated	N = 4: Naropin®; 150 mg (30 mL)

Dose escalation of a single postsurgical administration of TLC590 will be performed using sequential dose levels starting at 190 mg up to 760 mg, as compared with Naropin® 150 mg (5 mg/mL) via infiltrative local administration in adult subjects following unilateral Lichtenstein inguinal hernia repair surgery. Dose escalation

will be determined by review of treatment-related adverse events and all serious AEs (SAEs) by a safety monitoring committee (SMC); PK data will also be reviewed only by the SMC at the end of each cohort to assess systemic exposure to total and free (unbound) ropivacaine.

Number of Subjects:

Approximately 64 evaluable subjects in up to 4 cohorts of approximately 16 subjects per cohort will be enrolled in this study.

Treatment:

At the end of the surgery, prior to wound closure, a single infiltrative local dose of blinded study medication will be administered.

Study Duration:

The study duration will be approximately 60 days. Each subject will be screened within 28 days before blinded study medication administration. At the end of the surgery, prior to wound closure, a single infiltrative local dose of blinded study medication will be administered. The subject will remain in the clinic at least 48 hours after administration of blinded study medication, and each subject will be followed for 30 days.

Study Population:

Inclusion Criteria:

To be eligible for study entry, subjects must satisfy all of the following criteria:

1. Able and willing to provide a written informed consent, indicating that he/she is aware of the investigational nature of this study involved and willing to comply with the requirements of this study protocol.
2. Male or female between 18 and 65 years of age, inclusive.
3. Scheduled to undergo a primary, unilateral Lichtenstein inguinal hernia repair with mesh, and be able to use the anesthesia regimen.
4. Have an American Society of Anesthesiology (ASA) Physical Status Classification of 1 or 2.
5. Female subjects are eligible only if all of the following apply:
 - Not pregnant (female subjects of childbearing potential must have a negative serum pregnancy test at Screening and negative urine pregnancy test at Baseline before randomization);
 - Not lactating;
 - Not planning to become pregnant during the study;
 - Commits to the use of an acceptable form of birth control or be surgically sterile; or be at least 2 years post-menopausal; or is practicing double-barrier contraception; or practicing abstinence (must agree to use double-barrier contraception in the event of sexual activity); or using an insertable, injectable, transdermal, or combination oral contraceptive approved by the FDA for greater than 2 months prior to Screening visits and commits to the use of an acceptable form of birth control for the duration of the study and for 30 days from completion of the study.
6. Male subjects must be sterile (biologically or surgically) or commit to the use of a reliable method of birth control (e.g., must agree to use double-barrier contraception in the event of sexual activity) for the duration of the study until at least 1 week after the administration of blinded study medication.
7. Have a body mass index $\leq 35 \text{ kg/m}^2$.

Statistical Analysis:

No formal sample size calculation will be performed, but rather, the number of subjects per cohort is based on previous experience with other drugs for first-in-human trials and is generally considered adequate for determination of tolerability and PK characterization.

NPRS scores following rescue analgesics will be imputed by the windowed worst observation carried forward. The worst NPRS score prior to each rescue analgesic will be carried forward within the following 4-hour window. If the pain intensity score for the windowed observation is higher than the worst observed score, it will not be replaced. Missing NPRS scores will be imputed via the last observation carried forward (LOCF) using the last observed scores. Sensitivity analyses on NPRS related endpoints will be performed by imputing data following rescue analgesics using LOCF. The NPRS scores just prior to the rescue analgesics will be carried forward for all subsequent scheduled assessments.

Analysis of variance (ANOVA) or a Kruskal-Wallis test (if the normality assumption is not met) will be used to assess the overall difference among treatments for NPRS at rest and with movement, AUC of NPRS at rest and with movement, the total postoperative consumption of rescue analgesics, and the average daily rescue analgesic consumption.

The Kaplan-Meier method will be used to analyze time to the first postoperative use of rescue analgesic, and time to the first postoperative use of rescue opioid. Comparison of the survival curves among treatments will be assessed by a log-rank test.

Chi-square test or Fisher's exact test will be used to assess the overall differences among treatments for the proportions of subject who are opioid free, subjects who used no rescue analgesics, and subjects who used no postoperative antiemetic therapy, and PGA.

All the exploratory endpoints will be summarized descriptively.

Blood concentrations of ropivacaine (unbound and total) will be descriptively summarized at each scheduled time of PK sampling by treatment. PK parameters will be derived by non-compartmental analysis.

The dose-exposure relationship of TLC590 will be evaluated by the tabulation of AUC and C_{max} parameters obtained from each dose level and displayed graphically. The power model will be used to investigate the dose proportionality for subjects who received the TLC590 treatment. The relative systemic bioavailability (including relative AUC and C_{max}) compared to Naropin[®] will be analyzed by using a general linear model (GLM). Exposure-response relationship between PK parameters and NPRS scores will be displayed graphically and will be evaluated accordingly.

Safety analysis will be based on all safety information collected including physical examination, surgical site assessment, vital signs assessments, clinical laboratory data, 12-lead electrocardiogram (ECG), AEs, and SAEs.

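### Do the different volumes listed for TLC590 and Naropin in cohorts 1, 2 and 4 break the double blind?

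*Combined protocol and SAP*

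**What the plan says.** Under Study Design, the Synopsis states: "This is a Phase I/II, randomized, double-blind, comparator-controlled, dose-escalation study". Allocation is 3:1 within cohorts of about 16, through a central web response system.

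The dose table gives the comparator as "N = 4: Naropin®; 150 mg (30 mL") in every cohort. The TLC590 arm begins at "N = 12: TLC590; 190 mg (10 mL") and goes to 20 mL in cohort 2, 30 mL in cohort 3 and 40 mL in cohort 4, or 25 mL in cohort 4 if the cohort 3 dose is not tolerated.

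Under Treatment, the product is again described as blinded: "a single infiltrative local dose of blinded study medication will be administered". This takes place as surgery finishes, with the wound still open. Pharmacokinetic (PK) results go only to the safety monitoring committee (SMC).

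The Synopsis mentions no syringe masking, no matching of volumes, no unblinded preparer or injector, and no separate assessor. It does not list the roles that are blinded.

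**The concern.** A 10 mL injection and a 30 mL injection are easy to tell apart. If the table shows what is injected, anyone who handles or watches the dose in cohorts 1, 2 or 4 can work out the arm. Central allocation conceals the assignment before dosing but does nothing about this. Restricting PK results to the committee protects one data stream only.

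If a person who saw the volume also rated outcomes, three items would be open to influence:

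- **Causality of non-serious adverse events.** Dose escalation "will be determined by review of treatment-related adverse events and all serious AEs (SAEs) by a safety monitoring committee (SMC"). For a non-serious event, the judgement of relatedness decides whether it enters that review, and safety and tolerability are the primary objective.
- **Surgical site assessment.** "Safety analysis will be based on all safety information collected including physical examination, surgical site assessment".
- **Rescue analgesia.** Rescue use is an endpoint and also alters the pain scores: "The worst NPRS score prior to each rescue analgesic will be carried forward within the following 4-hour window". Arm-dependent handling of rescue could therefore reach both the rescue results and the NPRS results.

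**Working it through.** All inputs come from the dose table and text of the Synopsis.

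**Planned size.** 4 cohorts × (12 + 4) = 64, made up of 48 on TLC590 and 16 on Naropin. This reproduces the plan's own total: "Approximately 64 evaluable subjects in up to 4 cohorts of approximately 16 subjects per cohort".

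**Listed volumes and strengths.** Concentration = mg / mL; difference = TLC590 mL − Naropin mL.

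| Cohort | TLC590 | Concentration (mg/mL) | Naropin (mL) | Difference (mL) | Ratio |
|---|---|---|---|---|---|
| 1 | 190 mg, 10 mL | 190/10 = 19 | 30 | −20 | 0.33 |
| 2 | 380 mg, 20 mL | 380/20 = 19 | 30 | −10 | 0.67 |
| 3 | 570 mg, 30 mL | 570/30 = 19 | 30 | 0 | 1.00 |
| 4 (main) | 760 mg, 40 mL | 760/40 = 19 | 30 | +10 | 1.33 |
| 4 (alternative) | 475 mg, 25 mL | 475/25 = 19 | 30 | −5 | 0.83 |

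Naropin is 150/30 = 5 mg/mL throughout. The volumes match only in cohort 3, whichever option is used in cohort 4.

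**Ceiling on exposure.** Cohorts 1, 2 and 4 hold 3 × 16 = 48 of 64 subjects (75%): 3 × 12 = 36 of 48 on TLC590 and 3 × 4 = 12 of 16 on Naropin.

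**What the constant 19 mg/mL shows.** The table is consistent with one product strength given in increasing amounts. Undiluted injection is the natural reading. However, the mL figures are not labelled as final injected volume, and the same ratio would appear if they were drug-product volumes before any matching step. The arithmetic cannot separate the two readings. On the natural reading, unequal volumes simply follow from escalating a fixed-strength product against a fixed comparator.

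**From volume to bias.** Two conditions are needed: a person sees the volume, and the same person makes or influences a rating. The first is likely for whoever prepares and injects. The second is neither stated nor excluded. Dosing happens in the operating room; the ratings at issue are postoperative, over a stay of at least 48 hours and follow-up to 30 days. If the second condition fails, the number of affected ratings is zero. If it holds for every subject in the unequal cohorts, the number of affected subjects is 48. The documents give nothing to place the truth between 0 and 48, and nothing from which the size or direction of any bias could be calculated.

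**The case for a change.** The strongest case for acting is that the Synopsis itself prints the revealing volumes beside the double-blind label, that one sentence would settle the matter, and that the earliest escalation decisions are the most exposed. All 16 subjects in cohort 1 and all 16 in cohort 2 are in unequal-volume cohorts. This is so whether the committee reviews each cohort alone or adds them up. After cohort 3 the share would be 32 of 48 if review is cumulative, or 0 of 16 if it is by cohort; the Synopsis does not say which applies to adverse events.

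The arithmetic stands, and so does the observation that the Synopsis describes no masking method. The inference does not go further. These counts show where a rating could be influenced, not that any is. Serious adverse events and PK data reach the committee whatever anyone thinks about causality, so escalation does not depend only on the judgement at risk.

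The argument also relies on silence in a synopsis. The roles of those who prepare, inject and assess normally belong in protocol sections on blinding and administration, which are not part of the text checked here. The most that silence supports is a question to the sponsor. Prescribing who should rate, or how sites should staff, would mean redesigning arrangements that have not been seen, at about 2 centres whose staffing the documents do not describe.

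**Conclusion.** No change to the plan follows. The listed volumes differ in cohorts 1, 2 and 4, covering up to 48 of 64 subjects, and the Synopsis does not explain how volume is concealed. That does not contradict the double-blind label: a trial can be double-blind for subjects and outcome assessors while those who prepare and inject know the arm. No stated rule gives a wrong result, and no endpoint or analysis is misdefined. The gap is one that a site would fill sensibly by keeping the injector out of the ratings.

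This conclusion rests on two assumptions. The first is that the people who see the dose do not also rate adverse event causality or the surgical site, or collect pain scores and the PGA. The second is that the injected volume is not shown on records that assessors use. The Synopsis neither confirms nor denies either. If the protocol body, or practice at the sites, showed that the operator also makes these ratings, the point would become a real weakness in the safety and rescue data of three cohorts and would need to be reopened.

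### Can a pain score lowered by rescue medication be carried into later gaps, and must the synopsis rule this out?

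*Combined protocol and SAP*

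**What the plan says.** All the relevant text is in the Combined protocol and SAP, section 3 Synopsis.

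- Rescue rule (Statistical Analysis): "The worst NPRS score prior to each rescue analgesic will be carried forward within the following 4-hour window". Its exception: "If the pain intensity score for the windowed observation is higher than the worst observed score, it will not be replaced".
- Missing-score rule, stated next: "Missing NPRS scores will be imputed via the last observation carried forward (LOCF) using the last observed scores".
- Sensitivity analysis: "Sensitivity analyses on NPRS related endpoints will be performed by imputing data following rescue analgesics using LOCF", with the detail that "The NPRS scores just prior to the rescue analgesics will be carried forward for all subsequent scheduled assessments".
- Endpoints affected: NPRS itself and "AUC of NPRS at rest and with movement", compared among treatments by ANOVA or Kruskal-Wallis.
- Analgesic efficacy against Naropin is a secondary objective (Objectives). The primary one is safety and tolerability.
- Under Study Duration: "The subject will remain in the clinic at least 48 hours after administration of blinded study medication".

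The synopsis does not say which imputation step runs first. Nor does it say whether LOCF draws on recorded or window-adjusted scores.

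**The concern.** The rescue rule exists because a low score soon after rescue reflects the rescue drug rather than the study treatment. The exception uses *observed* for scores as recorded, so LOCF from observed scores can be read the same way. A low score that the plan refuses to use at its own time point would then fill the next gap.

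A window-adjusted score is never below the recorded score at the same time point. Carrying the recorded one therefore gives an equal or lower AUC than carrying the adjusted one. If Naropin subjects need more rescue, their AUC falls more and the contrast with TLC590 tends to narrow. Two programmers could also obtain different AUCs from the same data. The sensitivity analysis changes the rescue rule as a whole, so it would not isolate this choice.

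**Working it through.** The available text gives no AUC figure to reproduce, and no assessment times, missing rate, rescue rate or variance. From the documents come the 4-hour window, the two rules and the group sizes (12 TLC590 and 4 Naropin per cohort, four cohorts). All else below is assumed. *Literal* means LOCF of recorded scores; *adjusted* means LOCF of window-adjusted scores; *complete* means the windowed rule applied with nothing missing.

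**One subject.** AUC = sum of (y_i + y_{i+1})/2 × (t_{i+1} − t_i), at 0, 1, 2, 4, 6, 8, 12, 24, 36 and 48 h. Scores are 4, 5, 6, 7, 8 up to 6 h. Rescue comes just after 6 h; 3 is recorded at 8 h (windowed to 8); then 6, 5, 4, 3.

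- 0–6 h: 4.5 + 5.5 + 13 + 15 = 38. 6–8 h: 16. Running total 54.
- Complete: 54 + 28 + 66 + 54 + 42 = 244.
- Only 12 h missing, literal (3): 54 + 22 + 48 + 54 + 42 = 220, error −24.
- Only 12 h missing, adjusted (8): 54 + 32 + 78 + 54 + 42 = 260, error +16.
- All missing from 12 h, literal: 54 + 22 + 3 × 36 = 184, error −60.
- All missing from 12 h, adjusted: 54 + 32 + 8 × 36 = 374, error +130.
- Planned sensitivity analysis for this subject: 8 carried from 6 h to 48 h, 38 + 8 × 42 = 374.

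The adjusted reading is closer for the single gap, and the literal reading is closer for the terminal gap. Adjusted LOCF overshoots there because it holds the worst score for 40 hours after the 8 h assessment, although the rescue rule limits it to 4.

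**Arms.** Simulation with 200,000 subjects per arm on the same schedule, subject SD 1.5 and residual SD 1. Rescue follows a score of at least c with probability q and lowers recorded scores by d for 4 hours. (c, d, q) is (5, 2, 0.5) mild, (5, 3, 0.7) middle and (4, 5, 0.9) strong. Differences in mean AUC, Naropin minus TLC590, with 20% missing:

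| Setting | Complete | Literal (error) | Adjusted (error) |
|---|---|---|---|
| Scattered, mild | 47.6 | 47.5 (−0.1) | 49.2 (+1.6) |
| Scattered, middle | 46.4 | 45.4 (−1.0) | 47.7 (+1.3) |
| Scattered, strong | 44.8 | 42.7 (−2.1) | 46.1 (+1.3) |
| Dropout, mild | 47.6 | 47.4 (−0.2) | 48.1 (+0.5) |
| Dropout, middle | 46.4 | 45.3 (−1.1) | 46.7 (+0.3) |
| Dropout, strong | 44.8 | 42.4 (−2.4) | 44.3 (−0.5) |

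Literal is closer in three of the six settings. Adjusted enlarges the TLC590 advantage in five.

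**Scale.** With an AUC SD of about 72, 12 TLC590 subjects and 16 pooled Naropin subjects (pooling assumed), SE = 72 × √(1/12 + 1/16) = 27.5. The largest literal error is 2.4/27.5 = 0.09 SE. The largest gap between the two readings is 46.1 − 42.7 = 3.4, or 3.4/27.5 = 0.12 SE.

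**Second set-up.** On a different assumed schedule, with 2–10% scattered gaps and 0–10% dropout, about 3–16% of subjects were affected. Literal mean AUC was 0.6 to 6.3 below adjusted, on means of about 165–170. There, a missing score inside a window was set to the worst prior score. When it follows a kept higher score, that convention can reverse the order of the two readings; the largest reversal was 4 points.

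**The case for a change.** The strongest case for a change is that the text is ambiguous, one sentence would settle it, and settling it before unblinding removes discretion.

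For the level of AUC, as opposed to the arm difference, adjusted LOCF usually does better. With 5–20% scattered gaps, literal is off by −0.2% to −4.6% and adjusted by +0.2% to +1.2%. With 5–20% dropout the figures are −0.5% to −6.0% and −0.3% to −1.6%. If the worst prior score is taken only from available scores, scattered gaps give literal −0.3% to −5.6% and adjusted −0.4% to +0.6%, and the literal arm difference shrinks by up to 3.2 points (3.2/27.5 = 0.12 SE).

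Groups are also small. In the worked example the choice moves one subject by 260 − 220 = 40 or 374 − 184 = 190 points, hence a 12-subject mean by 40/12 = 3.3 or 190/12 = 15.8.

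The ambiguity stands, and so does the advantage for mean level. But the 15.8 needs a subject whose scores stop early, straight after a rescue window, during a stay of at least 48 hours in the clinic. In that case the adjusted value is the worse one: it errs by 130/12 = 10.8 on the group mean, against 60/12 = 5 for the literal value. Replacing LOCF by interpolation for gaps between scores would go beyond curing the ambiguity. With available scores only it gives −0.1% to −1.3%, no better than adjusted LOCF.

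**Conclusion.** No change is called for. What is missing is a processing order in a synopsis, which analysts fill sensibly. The windowed rule is stated first and the missing-score rule second, and applying them in that order keeps replaced scores out of LOCF. The harm needs the other reading of *observed*. Only the synopsis was available, so fuller text may already settle the point.

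Neither reading is plainly right. One carries a rescue-lowered score into a gap; the other carries the worst score past the plan's own 4-hour limit. Reasonable statisticians differ on this. The planned sensitivity analysis already gives an NPRS result free of rescue-lowered scores, though it does not isolate the choice.

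The effect is zero when nothing is missing. Under the assumed inputs it is about 0.1 SE on the arm difference even with 20% missing. It falls on a secondary objective in a trial with no formal sample-size calculation. The size rests on the assumed schedule, rescue pattern, variance and missing rates. A group with several early terminal gaps directly after rescue would show more, but the adjusted rule would not be a dependable cure there.

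### Every missing pain score is filled by LOCF, and no analysis in the synopsis tests that assumption: a minor gap that is cheap to close

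*Combined protocol and SAP*

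**What the plan says.** All references are to the synopsis (section 3) of the combined protocol and SAP, which is the text available for this review.

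Under Statistical Analysis there are two separate rules for NPRS scores:

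- After rescue: "The worst NPRS score prior to each rescue analgesic will be carried forward within the following 4-hour window".
- Missing for any reason: "Missing NPRS scores will be imputed via the last observation carried forward (LOCF) using the last observed scores".

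One sensitivity analysis is planned: "Sensitivity analyses on NPRS related endpoints will be performed by imputing data following rescue analgesics using LOCF". It works as follows: "The NPRS scores just prior to the rescue analgesics will be carried forward for all subsequent scheduled assessments".

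The filled scores feed the comparisons of NPRS and of "AUC of NPRS at rest and with movement" among treatments, by ANOVA or Kruskal-Wallis. These serve a secondary objective: "To evaluate analgesic efficacy of TLC590 compared with Naropin® for postsurgical pain management in subjects with inguinal hernia repair surgery". On group size: "Each cohort will comprise 12 subjects receiving a dose of TLC590 and 4 subjects receiving active comparator drug".

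**The concern.** LOCF assumes that a subject's pain would have stayed at its last recorded value. After a single infiltration at the end of surgery this is unlikely: pain may rise as the block wears off and fall as the wound heals. The AUC given to a subject whose scores stop then depends partly on where on that course the last score happened to fall. The same rule fills an isolated gap from the earlier score even when a later score exists.

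The planned sensitivity analysis addresses a different question, the handling of scores after rescue. It also carries a score forward. A reader who sees the two analyses agree could take the result as robust to missing scores, although that was never tested. With about 12 subjects per TLC590 dose, one or two incomplete records can move an arm mean, and single imputation enters filled values into the ANOVA as if they had been observed.

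**Working it through.** **1. What the documents give.** No withdrawal rate, NPRS schedule, AUC window, SD, target difference or power appears in the synopsis, so there is no figure to reproduce for this point. The group sizes agree with the stated total: 4 × (12 + 4) = 64, with 4 × 4 = 16 Naropin subjects if cohorts are pooled. Pooling is an assumption; the synopsis does not state it. All curves, time grids and windows below are also assumptions.

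**2. Formula.** With last score y(w) at time w and window end T:

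LOCF AUC = (observed AUC from 0 to w) + y(w) × (T − w).

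The error is y(w) × (T − w) minus the true area after w. It is zero if pain is flat after w or, by coincidence, if the later average equals the last score.

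**3. Rise-and-fall curve (assumed).** NPRS of 1, 1.5, 2, 3.5, 5.5, 6, 5, 4, 3, 2.5, 2 at 0, 1, 2, 4, 8, 12, 24, 36, 48, 60, 72 h. The complete trapezoidal AUC over 0–72 h is 271.5.

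| Last score | Observed part | Carried part | LOCF AUC | Error |
|---|---|---|---|---|
| 2 h | 3.0 | 2 × 70 = 140 | 143.0 | −47% |
| 4 h | 8.5 | 3.5 × 68 = 238 | 246.5 | −9% |
| 8 h | 26.5 | 5.5 × 64 = 352 | 378.5 | +39% |
| 12 h | 49.5 | 6 × 60 = 360 | 409.5 | +51% |
| 24 h | 115.5 | 5 × 48 = 240 | 355.5 | +31% |
| 36 h | 169.5 | 4 × 36 = 144 | 313.5 | +15% |
| 48 h | 211.5 | 3 × 24 = 72 | 283.5 | +4% |

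One such subject moves a 12-subject arm mean by −47.3%/12 = −3.9% to +50.8%/12 = +4.2%. With a 0–48 h window (complete AUC 211.5), a last score at 36 h gives 217.5, an error of +3%.

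**4. Other shapes.** On a steadily falling curve (from 7 at 0 h to 2 at 72 h; complete AUC 268.1) the error is always upward: 468.6 (+75%) for a last score at 2 h, down to 295.1 (+10%) at 36 h. On a flat curve it is zero. Error in both directions therefore needs a rise and a fall; dependence on time needs only a curve that is not flat.

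**5. Isolated gap, curve of step 3, 8 h score missing.** True area from 4 to 12 h: 18 + 23 = 41. LOCF puts 3.5 at 8 h: 14 + 19 = 33, an error of −8. Interpolation gives (3.5 + 6)/2 × 8 = 38, an error of −3.

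**6. Does the planned sensitivity analysis react?** On the curve of step 3, over 0–72 h:

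- Never rescued, last score at 4 h: 246.5 in both analyses.
- Rescued at 12 h and lost at once: 409.5 in both.
- Rescued at 12 h, scored 3 at 24 h, then lost: main analysis 49.5 + 54 + 3 × 48 = 247.5; sensitivity analysis 409.5. The result changes, but only because a different score is carried forward.

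**7. Effect on the difference between arms.** A separate pair of assumed mean curves, one per arm, over 1–72 h gives these errors in time-averaged NPRS per withdrawn subject. They are illustrative inputs, and the curves themselves are not tabulated here.

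| Withdrawal | Naropin | TLC590 |
|---|---|---|
| 4 h | +0.03 | −0.96 |
| 8 h | +1.88 | −0.03 |
| 12 h | +1.88 | +0.15 |
| 24 h | +0.74 | +0.74 |

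Shift toward TLC590 = (Naropin error)/16 − (TLC590 error)/12, for one withdrawal per arm.

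- Same time in both arms: 4 h, 0.03/16 + 0.96/12 = 0.08; 8 h, 1.88/16 + 0.03/12 = 0.12; 12 h, 1.88/16 − 0.15/12 = 0.105; 24 h, 0.74/16 − 0.74/12 = −0.015.
- Largest of the 16 pairings: 1.88/16 + 0.96/12 = 0.20.
- Smallest: 0.03/16 − 0.74/12 = −0.06.
- Mean: (4.53/4)/16 − (−0.10/4)/12 = 0.071 + 0.002 = 0.07.

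**The case against.** The strongest case against the point is about size. Subjects stay in the clinic for at least 48 hours and the large errors need scores to stop within about 12 hours, so the trigger may be rare. Losses after 48 h cost little (+4% in step 3). Efficacy is secondary, no power is claimed, and the planned test is an overall comparison among treatments rather than the pairwise difference of step 7. Time to first rescue and the opioid-free proportion do not use imputed NPRS. All of this stands, and it makes the point minor. It does not supply the missing analysis.

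A reader might go further and infer that LOCF favours TLC590: Naropin subjects would be frozen at peak pain and TLC590 subjects while the block still works, giving 0.20 points against a difference of 0.47 in the same assumed curves. The documents do not support this. The 0.20 pairs the least favourable times out of 16 combinations; at 12 h and 24 h LOCF overstates pain on TLC590, and the range crosses zero. The documents give neither the curves nor the 0.47.

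It would also be too much to say that the time of withdrawal sets a subject's AUC, since the scores already observed count too. Nor does the rule mention withdrawal: it covers all missing scores, and withdrawal is one application of it.

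**Conclusion.** The gap holds on the text. LOCF is the only rule for missing NPRS scores, and the one sensitivity analysis varies post-rescue handling, itself by LOCF. Unless pain is flat after the last score, the filled AUC depends on when scores stop, and the synopsis contains no analysis that varies this.

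Its size and direction cannot be determined from the documents; they depend on the pain curve, the arm and the timing. The illustrative range is −0.06 to +0.20 points toward TLC590 (mean 0.07) for one withdrawal per arm. It rests on assumed curves, a 1–72 h window, pooling of the 16 Naropin subjects and equal weight on all pairings for the mean. Severity is minor: a cheap improvement, not a flaw that undermines the trial. Nor do the documents require replacing LOCF by within-arm multiple imputation as the main rule after the last score. With about 12 subjects per dose and a Kruskal-Wallis fallback, that is a trade-off.

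**What to change.** Two changes to the SAP:

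1. Where a missing score lies outside a rescue window and has observed scores on both sides, interpolate linearly instead of carrying the earlier score forward. For the AUC this is the same as applying the trapezoidal rule to the observed times.
2. For scores missing after a subject's last assessment, pre-specify a sensitivity analysis of NPRS and its AUC that does not use LOCF, and report it beside the LOCF result. A simple repeated-measures model, or multiple imputation by treatment under missing at random, would serve.

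The same paragraph should state which rule applies first when a score is both missing and within 4 hours of rescue; the synopsis does not.

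Cost: SAP wording and modest programming, with no new data and no change to trial conduct. At about 12 subjects per dose the model must be simple and its estimates will be imprecise. Reporting the added analysis as estimates with intervals avoids having to combine Kruskal-Wallis tests across imputations.
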